6.0 CRITERIA FOR SUBJECT ELIGIBILITY

6.1 Subject Inclusion Criteria

- Pathologic diagnosis of malignant pleural mesothelioma (MPM) confirmed at participating institution.
- Positive immunohistochemical staining for WT-1 (greater than 10% of cells).
- Completion of multimodality therapy. This must include surgical resection by either pleurectomy/decortication or extrapleural pneumonectomy. The surgery should be performed with the intent of complete resection, though patients with an R1 resection will still be eligible. Patients should have also received treatment with chemotherapy and/or radiation. Patients with an R2 resection are also eligible as long as the site of residual disease is treated post-operatively with radiotherapy.
- 4-12 weeks since completion of combined modality therapy.
- Age \geq 18 years
- Karnofsky performance status \geq 70%
- Hematologic parameters: Absolute neutrophil count \geq 1000/mcL, Platelets $>$ 50 K/mcL.
- Biochemical parameters: Total bilirubin \leq 2.0 mg/dl, AST and ALT \leq 2.5 x upper limits of normal, Creatinine \leq 2.0 mg/dl.

6.2 Subject Exclusion Criteria

- Pregnant or lactating women.
- Patients with active infection requiring systemic antibiotics, antiviral, or antifungal treatments.
- Patients with a serious unstable medical illness or another active cancer.
- Patients taking systemic corticosteroids.
- Patients with an immunodeficiency syndrome.

7.0 RECRUITMENT PLAN

This trial initially was designed to enroll a total of 78 patients (39 in each arm). With the early closure of the control arm, the total number of patients will be reduced to 60. This will take approximately 6 years to complete. Every effort will be made to include women and minorities in the research study.

MEMORIAL SLOAN-KETTERING CANCER CENTER IRB PROTOCOL

IRB#: 10-134 A(8)

Potential research subjects will be identified by a member of the patient's treatment team, the protocol investigator, or research team at the participating institution. If the investigator is a member of the treatment team, s/he will screen their patient's medical records for suitable research study participants and discuss the study and their potential for enrolling in the research study. Potential subjects contacted by their treating physician will be referred to the investigator/research staff of the study.

8.0 PRETREATMENT EVALUATION

Within 2 weeks of the first vaccination, patients will have the following:

- History and physical examination.
- CBC with differential.
- Comprehensive panel.
- Soluble mesothelin related protein (SMRP) level
- Serum B-hCG for women with reproductive potential.
- HLA typing (a specific HLA type is not required for participation).

Within 4 weeks of the first vaccination:

- CT scan of the chest.

9.0 TREATMENT/INTERVENTION PLAN

- Patients will be treated as outpatients.
- Treatment will be administered on weeks 0, 2, 4, 6, 8, and 10.
- All injections will be administered subcutaneously with sites rotated among extremities.
- Patients will be randomized to receive either non-specific immune therapy (Montanide adjuvant + GM-CSF) or GM-CSF plus the WT-1 peptide vaccine with Montanide adjuvant:

All patients will receive Sargramostim (GM-CSF) (70 mcg) injected subcutaneously on days 0 and -2 of each vaccination. Patients may self administer the Sargramostim (GM-CSF) on day -2 if they have been appropriately instructed on SQ injection administration. Patients will be informed of the expected reactions such as irritation at the injection site. Patients will keep a logbook noting the time and placement of the injection.

Patients will also receive 1.0 ml of emulsion with Montanide alone or with WT-1 peptides plus Montanide. It will be administered by a nurse (it may not be self-administered) subcutaneously to the same anatomical site as

MEMORIAL SLOAN-KETTERING CANCER CENTER IRB PROTOCOL

IRB#: 10-134 A(8)

the GM-CSF. This site will be marked by the patient or treating healthcare professional by a permanent marker pen.

10.0 EVALUATION DURING TREATMENT/INTERVENTION

T-cell Immune Response Assays

Peripheral blood 100 ml will be drawn immediately before vaccinations at baseline and on week 12. At each time point, 12 green top tubes and 1 red top tube of blood will be obtained. These samples will be delivered on the day of acquisition. All samples will be delivered to:

[name].
Memorial Sloan-Kettering Cancer Center
Mortimer B. Zuckerman Research Center: Z1945
[name]
New York, NY 10065

The blood samples obtained at baseline and week 12 will be tested for CD4 T cell proliferation, CD4 and CD8 T cell interferon release. See Appendix I for details on the techniques. The immunologic correlative blood samples described above may be collected at alternate time points if patients are required to come off study due to disease progression.

Clinical course: Refer to schema below:

	Baseline ¹	Week							
		0	2	4	6	8	10	12	Q 3 month ⁴
Informed consent	X								
History, medications, and adverse events recording	X		X		X			X	X
Physical exam	X		X		X			X	X
CBC	X				X			X	X
Comprehensive panel	X				X			X	X
Beta-hCG ^a	X								
HLA typing	X								
CT scan of chest	X							X ²	X ²
Immunology bloods	X							X ³	
SMRP level	X				X			X	X
WT-1 Vax/ Montanide + GM-CSF ^b		X	X	X	X	X	X		

^a For women with reproductive potential.

^b Sargramostim (GM-CSF) will be injected subcutaneously on day -2 and day 0 for each time point.

Amended: 7/14/15

MEMORIAL SLOAN-KETTERING CANCER CENTER IRB PROTOCOL

IRB#: 10-134 A(8)

¹ Baseline implies within two weeks of the first vaccination except imaging studies which will be within 4 weeks.
HLA typing could have been performed anytime.

² May be performed earlier if clinically indicated.

³ If a patient is removed from study prior to week 12 they will have their immunology blood work at the time of study removal.

⁴ For two years or until disease progression

- History and physical examination at baseline, at weeks 2, 6, and 12 and every 3 months thereafter for up to 2 years or until disease progression.
- CBC and comprehensive panel will be drawn at baseline, at weeks 6 and 12, and every 3 months thereafter for up to 2 years or until disease progression.
- CT scan of the chest will be performed at baseline and at week 12. Follow up CT scans will be performed every 3 months for two years or until disease progression.
- Note that all study procedures may be conducted within a +/- 3 day window in the first 12 weeks and within a +/- 7 day window in the subsequent weeks without being considered a study violation.

11.0 TOXICITIES/SIDE EFFECTS

Expected Toxicities

The expected toxicity with these doses of Montanide includes mild inflammation at injection sites and occasional fever. In rare patients, allergic reactions have been observed. The toxicities of Sargramostim (GM-CSF) at standard doses of 250ucg/m²/day for 5 to 14 days include inflammation at injection sites, edema, fluid retention, headache, myalgia, arthralgia, dyspnea, and allergic reactions. Patients with pre-existing renal and/or hepatic disorders may demonstrate elevations in serum creatinine or bilirubin/transaminases respectively. In this trial, a total of 140 micrograms will be injected with each vaccination cycle.

Potential Risks

Autoimmune or hypersensitivity reactions to components of the vaccine are theoretical possibilities, though unlikely. There have been no autoimmune or hypersensitivity reactions in patients vaccinated with other WT-1 peptides.

Criteria for Toxicity

Toxicity will be graded in accordance with the Common Toxicity Criteria, version 4.0 (CTCAE4.0) developed by the National Cancer Institute. <http://ctep.cancer.gov>.

Criteria for Treatment Cessation

Expected adverse events from the vaccine include local erythema, edema and itching. These are usually mild and may be observed after each administration of the vaccine. These symptoms will be treated symptomatically and will not require treatment interruptions or discontinuation.

MEMORIAL SLOAN-KETTERING CANCER CENTER IRB PROTOCOL

IRB#: 10-134 A(8)

In patients who develop a grade 2 allergic reaction consisting of generalized urticaria or evidence of systemic allergic reaction, vaccination will be discontinued and the patient will be taken off study.

Patients who develop Grade 3 or 4, toxicity that is considered possibly or probably related to the vaccine or any of its components will be taken off study.

Patients who develop evidence of autoimmune disorders or anaphylactic reaction considered to be possibly related to the vaccine will be taken off study.

12.0 CRITERIA FOR THERAPEUTIC RESPONSE/OUTCOME ASSESSMENT

Immune response: Immune responses will be measured by T cell proliferative response against WT-1 peptides. In patients with adequate samples, T cell gamma interferon release as measured by ELISPOT will be performed as well.

T cell responses ex vivo: Heparinized peripheral blood (100 ml) will be drawn prior to treatment and at week 12 during treatment as indicated in Section 10.0. If the patient is removed from study prior to week 12 they will have their blood sampled at the time of study removal. Peripheral blood lymphocytes (PBLs) will be tested for proliferation and gamma-interferon release by ELISPOT as described in Appendix I.

T cell proliferative and interferon release responses will be measured ex vivo in quadruplicate at each timepoint after challenge with the vaccinating peptide, an irrelevant control peptide, or no peptide. A response will be called positive for reactivity with the test peptides if the result is at least 2 fold higher for the test peptides as compared to the control peptides and statistically significant. While comparisons of positivity between timepoints in an individual patient will be attempted, expected differences in baselines (ie control responses) between timepoints may preclude conclusions about the magnitude of response as a result of vaccination. For assays preformed in [name] lab, immune data will be reviewed by an independent group of 2 or 3 investigators led by [name].

Radiographic assessment: In this study, patients will be receiving the WT-1 vaccine after completion of surgery plus chemotherapy and/or radiation. As a result, patients may not have evidence of disease at the time of enrollment, they may have residual pleural scarring from radiation, or they may have some residual disease if the resection was incomplete.

Response is not one of the parameters that will be assessed. Patients will have periodic CT scans, however, to monitor for disease progression which is the primary endpoint of the trial. The Modified Response Evaluation Criteria in Solid Tumors Group (Modified RECIST) criteria will be used, if needed, for measurements.³³ Progressive disease would include an increase in the sum of measurements over 20% if some residual disease is evident at the time of enrollment, or the development of new sites of disease.

Patients with a global deterioration of health status requiring discontinuation of treatment without objective evidence of disease progression at that time should be reported as "symptomatic deterioration." Every effort should be made to document the objective progression even after discontinuation of treatment.

MEMORIAL SLOAN-KETTERING CANCER CENTER IRB PROTOCOL

IRB#: 10-134 A(8)

Conditions that may define early death include patients that have died without documentation of disease progression and before it was time to conduct the first tumor reassessment. Inevaluable patients have received protocol treatment and did not have any follow-up assessment completed before initiation of alternative treatment.

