2.0 OBJECTIVES AND SCIENTIFIC AIMS

Primary Objective: To assess the 1-year progression free survival in patients treated with WT-1 analog peptide vaccine + GM-CSF or Montanide + GM-CSF after completion of combined modality therapy for MPM.

Secondary Objectives:

- 1) To confirm the immunogenicity of the WT-1 analog peptide vaccine in patients with MPM after completion of combined modality therapy.
- 2) To assess the utility of using the serum marker, soluble mesothelin related protein (SMRP), in monitoring patients with MPM for disease progression.

Amended: 7/14/15

MEMORIAL SLOAN-KETTERING CANCER CENTER IRB PROTOCOL

IRB#: 10-134 A(8)

- 3) To assess the overall survival of patients treated with WT-1 analog peptide vaccine + GM-CSF or Montanide + GM-CSF after completion of combined modality therapy for MPM.

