GM-CSF: GM-CSF has been used in a number of vaccines studies as an immunologic adjuvant with the presumed benefit mediated through effects on dendritic and other antigen-presenting cells. Several human vaccine studies in melanoma and other human malignancies have reported both encouraging immunologic and clinical results. More recently, two melanoma vaccine studies have reported a deleterious effect of GM-CSF when used as a vaccine adjuvant.^{25,26} While it is important to be cognizant of such a potential negative effect, this study uses a different vaccine with a different dose of GM-CSF in a different disease. Other peptide vaccines studies have used GM-CSF as an adjuvant without negative results.^{27,28}

Rationale for study design: We have chosen to test the efficacy of our WT-1 peptide vaccine in MPM patients who have minimal disease burden after completion of multimodality therapy, but remain at exceedingly high risk for recurrence. Designing a clinical trial to show a benefit from a cancer vaccine is notoriously challenging. Single arm studies showing prolonged time to progression or survival are fraught with patient selection bias. The only way to avoid this bias and show that a vaccine has provided a benefit is by conducting a randomized trial. In this case, we chose to study treatment with Montanide and GM-CSF in one arm. Some immunologists would argue that the use of immune stimulants, such as GM-CSF, could provide a non-specific immune response resulting in some anti-tumor effects. Indeed, this has been observed in studies in prostate cancer and melanoma^{29,30}. The other arm will receive treatment with GM-CSF plus more targeted immunotherapy with WT-1 vax/Montanide. Although the size of this randomized phase II trial precludes direct comparison of the two arms, it will provide valuable information regarding the utility of immunotherapy in the adjuvant setting for this disease. If this study yields promising results, a larger randomized phase III trial would be warranted for confirmation of benefit from WT-1 vax.

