14.0 BIOSTATISTICS

This is a double-blinded, randomized phase II trial assessing the efficacy of vaccination with the WT-1 vaccine plus the immunologic adjuvant Montanide ISA 51 VG plus GM-CSF (Arm A) to non-specific immune stimulation with Montanide and GM-CSF alone as a control (Arm B) in patients who have completed multimodality therapy including surgery (plus at least one of chemotherapy and radiation) for malignant pleural mesothelioma. There is no intended comparison between the two arms. The literature lacks solid historical control data in this population. One of the reasons for accruing patients to the control arm is to further define the progression rate in a control population.

The primary endpoint is 1-year progression free survival (PFS) rate from start of WT-1 vaccine. Patients will be randomized according to the randomization procedure in Section 15.2 at the time of enrollment on the vaccine study which is after completion of multimodality therapy. PFS will be calculated from the time of randomization to first evidence of disease recurrence or death of any cause. Based on prior multicenter trials of neoadjuvant chemotherapy followed by extrapleural pneumonectomy and hemithoracic radiation (see table below), the 1-year PFS after completion of multimodality therapy is expected to be 50%. An improvement in 1-year PFS to 70% would be of interest for the vaccine arm (Arm A).

Author	Country	Year	Study type	N	Med time to recurrence (mo)
Weder ³⁴	Switzerland	2004	Prospective	19	16.5
Rea ³⁵	Italy	2007	Prospective	21	16.3
Weder ³⁶	Switzerland	2007	Prospective	61	13.5
Batirel ³⁷	Turkey	2008	Prospective	20	10
Bolukbas ³⁸	Germany	2009	Prospective	35	15.8
Krug ⁴	US	2009	Prospective	77	10.1

Amended: 7/14/15

MEMORIAL SLOAN-KETTERING CANCER CENTER IRB PROTOCOL

IRB#: 10-134 A(8)

Van Schil ³⁹	EORTC	2009	Prospective	59	13.9
Hasani ⁴⁰	Australia	2009	Retrospective	36	12.5

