Toxicities will be tabulated according to the NCI Common Toxicity (version 4.0). Immunologic response will be assessed for all patients. Immune responses will be evaluated at baseline and at week 12 by CD4 T cell proliferation, CD4 and CD8 T-cell interferon release. A response will be called positive for reactivity with the test peptides if the result is at least 2 fold higher for the test peptides as compared to the control peptides. Overall survival will be calculated from date of randomization to date of death or last follow-up. Progression free survival will be calculated from date of randomization to date of progression, death or last

MEMORIAL SLOAN-KETTERING CANCER CENTER IRB PROTOCOL

IRB#: 10-134 A(8)

follow-up. Survival distributions for each arm will be estimated using Kaplan-Meier methodology.

Measurement of the tumor marker, SMRP, is an exploratory aspect of this study to determine whether elevating levels on serial measurements correlates with recurrence as determined using traditional CT scan imaging.

Originally, a total of 78 patients were planned for accrual to this study. Due to the interim analysis that led to early closure of the control arm, total sample size was lowered to 60 patients. Enrollment is anticipated to take 6 years. Additional centers will enroll patients on an identical protocol under their own IND, and the data will be pooled with those from MSKCC for the final analysis.

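### Immunogenicity is judged only within patients; the same WT-1 assays from the randomised adjuvant-only arm should give an exploratory between-arm estimate

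*Combined protocol and SAP*

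**What the plan says.** Section 2.0 lists as the first secondary objective "To confirm the immunogenicity of the WT-1 analog peptide vaccine in patients with MPM after completion of combined modality therapy". No hypothesis, threshold or sample size goes with it.

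Section 12.0 calls a sample positive when the result is "at least 2 fold higher for the test peptides as compared to the control peptides and statistically significant". This is a contrast within one patient at one timepoint and needs no change from baseline. Section 14.0 repeats the twofold rule but leaves out the significance condition.

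On change over time, Section 12.0 says: "While comparisons of positivity between timepoints in an individual patient will be attempted", and then adds the caution that "expected differences in baselines (ie control responses) between timepoints may preclude conclusions about the magnitude of response as a result of vaccination".

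Both arms supply the data. Section 14.0 states "Immunologic response will be assessed for all patients" and "Immune responses will be evaluated at baseline and at week 12 by CD4 T cell proliferation, CD4 and CD8 T-cell interferon release". Section 10.0 schedules a 100 ml draw at each of the two timepoints, with no distinction by arm.

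Section 14.0 also states, without limiting it to any endpoint, "There is no intended comparison between the two arms". Section 3.0 gives the reason: "the size of this randomized phase II trial precludes direct comparison of the two arms". The control arm's stated statistical purpose is to describe the progression rate. No visible text uses its WT-1 assays as a comparator.

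**The concern.** Reactivity to WT-1 peptide at week 12 need not come from the vaccine peptides. Section 3.0 reports that one of five tested HLA-A0201 patients in the pilot was already reactive before vaccination. Section 6.1 admits patients 4 to 12 weeks after multimodality therapy, when a WT-1-specific response may be recovering. Section 9.0 gives GM-CSF and Montanide to everyone, and these could boost an existing WT-1 response without any peptide.

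A proportion positive in the vaccine arm alone mixes these sources with the peptide effect. The trial has a randomised arm that differs only in the peptides and is assayed identically, but the analysis plan gives those assays no role in secondary objective 1. At stake is whether the trial can say that the peptides, and not the setting or the adjuvants, produced the reactivity it reports.

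**Working it through.** **1. What each comparison can remove.**

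| Source of reactivity at week 12 | Control peptide, same sample | Baseline sample, same patient | Adjuvant-only arm |
|---|---|---|---|
| Non-specific activation, assay background | Yes, at least in part | In part | Yes |
| WT-1 reactivity present before vaccination | No | Yes for positivity; magnitude doubtful (Section 12.0) | Yes, on average |
| WT-1 reactivity recovering after therapy | No | No | Yes, on average |
| WT-1 reactivity boosted by GM-CSF plus Montanide | No | No | Yes, on average |

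The first two comparisons are planned. The third is not.

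**2. The plan's own figures.** There are none for immune response. The design figures concern PFS and reproduce: with 39 patients and success at 24 or more, P(X ≥ 24) is 0.0998 at 50% and 0.906 at 70%, against stated errors of 0.10 and 0.10.

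**3. Size of the attribution problem.** The documents give no week-12 background rate, so 10% to 30% is assumed (pilot pre-vaccination reactivity was 1/5 = 20%, exact 95% CI 0.5% to 72%). Expected positives with no peptide effect are 39 × 0.10 = 3.9, 39 × 0.20 = 7.8 and 39 × 0.30 = 11.7.

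**4. What a between-arm comparison could show.** Inputs:
- Vaccine-arm rate: 67%, from six responders and three non-responders named for the pilot in Section 3.0. The denominator of nine is inferred, and the exact 95% CI for 6/9 is 30% to 93%. Rates of 50% and 40% are therefore also tried.
- Control-arm rate: 10%, 20% or 30%, assumed.
- Controls: 20, assumed. The revised total of 60 has no stated split; 60 − 39 = 21 if the vaccine arm fills.

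Power = Σₐ Σ_b Bin(a; n₁, p₁) · Bin(b; n₂, p₀) · 1{two-sided Fisher p ≤ 0.05}, enumerated exactly:

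| Vaccine v control | 20 v 20 | 39 v 20 |
|---|---|---|
| 67% v 10% | 0.96 | 0.99 |
| 67% v 20% | 0.79 | 0.92 |
| 67% v 30% | 0.51 | 0.72 |
| 50% v 20% | 0.41 | 0.56 |
| 40% v 10% | 0.49 | 0.65 |
| 40% v 20% | 0.19 | 0.27 |

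The 39 v 20 column includes vaccine patients who may have enrolled after the control arm closed. With missing assays, 67% v 20% falls to 0.60 at 15 per arm and 0.54 at 12 per arm. For reference, PFS of 70% v 50% at 39 per arm has power 0.35 on the same test.

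**5. Precision.** Half-width of the 95% CI = 1.96 × √[p₁(1 − p₁)/n₁ + p₀(1 − p₀)/n₂]. For 67% v 20%:
- 20 v 20: 1.96 × √(0.2211/20 + 0.16/20) = 0.27
- 39 v 20: 1.96 × √(0.2211/39 + 0.16/20) = 0.23

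**The case against.** **The absence of a comparison is deliberate.** Section 14.0 rules it out in general terms, and objective 1 carries no hypothesis, so description is a defensible aim. Nothing prevents tabulation by arm. This stands, and it is why the addition should be an exploratory estimate. But the size rationale in Section 3.0 is not argued separately for a laboratory endpoint.

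**Section 12.0 could be read as admitting that the pre/post comparison is uninterpretable, or cannot be attributed to vaccination.** The text does not go that far. It says that shifting assay controls may prevent conclusions about magnitude, and comparison of positivity is still to be attempted.

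**A reader might infer that nothing but the adjuvant-only arm guards against non-specific effects.** That is also too strong. Each sample is tested in quadruplicate against the vaccinating peptide, an irrelevant peptide and no peptide. General activation should raise the control wells as well, so part of it is already removed. What remains is WT-1-specific reactivity not caused by the peptides.

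**A reader might conclude that the size argument does not apply to immune response.** That holds only if the vaccine rate is near 67%, an inferred small-sample figure. The pilot also used a different schedule, mostly in unresectable or relapsed disease, and counted a more than twofold rise in stimulation index, not conversion from negative to positive. At 50% v 20% or below, size is a real limit here too.

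**Data will be incomplete.** ELISPOT depends on adequate samples, and patients removed early are sampled at other times.

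**The T-cell assay appendix was not available for this review.** Section 12.0 cites it for technique, so an analysis rule there is unlikely but cannot be excluded.

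**Conclusion.** The concern holds in a limited form. As written, the plan can report how many patients react to WT-1 peptides, and perhaps how many became positive. It has no step that separates a peptide effect from WT-1-specific recovery or an adjuvant effect, and only a tentative one for pre-existing reactivity. The randomised control assays that could do this are collected and left without a stated use.

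The size of the problem rests on an assumed background of 10% to 30%, or about 4 to 12 of 39 patients. A between-arm comparison would be informative for a large difference (0.79 at 20 v 20 for 67% v 20%) and weak for a moderate one (0.41 for 50% v 20%, 0.19 for 40% v 20%). The number of controls, both arms' rates and complete assays are all assumptions. These figures support adding an exploratory estimate. They do not support a confirmatory test, or a claim that the planned within-patient data are worthless.

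**What to change.** In Section 14.0, under secondary objective 1:

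- Report baseline and week-12 positivity by arm, using the Section 12.0 definition with its significance condition, and bring the Section 14.0 wording into line.
- Estimate the between-arm difference in the proportion positive at week 12 and not at baseline, with a 95% CI. Label it exploratory, with Fisher's exact test as supportive. Conversion is itself a between-timepoint classification, so the positivity rates at each timepoint should be shown beside it.
- Base this on patients randomised while both arms were open. Show all vaccine patients as a secondary set, because any enrolled after the control arm closed have no concurrent controls.
- State the number with evaluable assays in each arm, and how samples taken at early removal are handled.
- Optionally, analyse log week-12 stimulation index or spot count adjusted for the log baseline value, with a stated rule for zero counts.

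PFS stays without a between-arm comparison. The cost is a paragraph and one table, with no new patients, samples or assays. The drawback is a wide interval, about ±27 points at 20 v 20 and ±23 points at 39 v 20 for 67% v 20%.
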